6. STATISTICAL METHODS

6.1. Data processing

The analyses will be computed with SAS Version 9.4 TS Level 1M6 Copyright (c) 2016 by SAS Institute Inc., Cary, NC, USA.

6.2. Description

The number of available data and/or the number of missing data will be given and the following descriptive statistics will be provided:

- For quantitative parameters: mean, standard deviation (SD), median, Q1, Q3, extreme values (min and max).

In this case, calculated statistics (mean, standard deviation, median, Q1, Q3) will generally be displayed with one more significant figure than the observed data, unless the described variable necessitates less precision.

- For qualitative parameters: number and percentage of each modality.

Usually, one decimal digit will be given. A second decimal digit could be provided to improve the display, if required.

6.3. Statistical/Analytical issues

6.3.1. Significance level

All statistical analyses will be performed at the 0.05 global significance level (type I error rate), using two-sided tests.

Because of the exploratory nature of the study, all the statistical results have to be considered within a descriptive perspective and not as inferential issues. No adjustment for Type I error is done. P-values of statistical tests will be provided for information only.

6.3.2. Interim analysis

No interim analysis will be performed.

6.3.3. Handling of dropouts and missing data

a) Repositioning of visits

Not applicable.

b) Partially filled scales (if applicable)

The SNOT-22 questionnaire can be analysed when there are missing data, if less than 50% of items are missing. A higher proportion of missing items makes the questionnaire unsuitable for statistical analysis.

For the SNOT-22 questionnaire with missing data, provided more than 50% of items have been completed, a total score will be imputed from the completed items (Hopkins, Gillett, Slack,

Lund, & Browne, 2009) by use of a mean individual technique (Roth, Switzer, & Switzer, 1999): for a given subject, if an item is missing, its value will be imputed by the mean of the non-missing items of SNOT-22 for the same subject.

c) Missing data (other than dropouts)

Missing data will not be estimated and will be treated as missing data for the statistical analysis.

Concerning missing dates, see §6.4

d) Dropouts

Subjects from Safety Set who prematurely discontinued the study will be included in the analysis.

No method will be applied to replace missing data.

6.4. General conventions and/or calculated variables

6.4.1. Subject reference start/end dates

For each subject, the reference dates will be the following:

- The reference start date is the date of inclusion visit.
- The reference end date is the date when subject was determined to have ended the trial.

6.4.2. Computation of a duration

The formulae below will be generally used:

- Duration (in days) = Date#2 – Date#1 + 1 day

6.4.3. Missing dates of inclusion visit or end of study

Missing dates of the inclusion visit will be considered equal to the inclusion date.

Missing dates of end of study will be reviewed by the members of the Validation Committee and extrapolated using all information recorded.

6.4.4. Missing start/end dates of adverse events / incidents / expected side effects

In the following paragraphs, adverse events, incidents and expected side effects will be referred to as “adverse events” for ease of reading.

a) Start date

Completely missing date: it will be estimated by the reference start date.

If the day and the month are missing:

- If the year = year of reference start date, it will be estimated by the reference start date
- If the year < year of reference start date, it will be estimated by the 31st December

- If the year > year of reference start date, it will be estimated by the 1st January

If only the day is missing:

- If the month/year = month/year of reference start date, it will be estimated by the date of reference start date
- If the month/year < month/year of reference start date, it will be estimated by the last day of the month
- If the month/year > month/year of reference start date, it will be estimated by the first day of the month

If after imputation, the estimated start date is after the end date of the adverse event, it will be replaced by the end date of the adverse event.

b) End date

Note: the following rules concern events that are not “ongoing” at the end of the study.

Completely missing date: it will be estimated by the reference end date

If the day and the month are missing:

- If the year = year of reference end date, it will be estimated by the reference end date
- If the year < year of reference end date, it will be estimated by the 31st December
- If the year > year of reference end date, it will be estimated by the 1st January

If only the day is missing:

- If the month/year = month/year of reference end date, the it will be estimated by the reference end date
- If the month/year < month/year of reference end date, the it will be estimated by the last day of the month
- If the month/year > month/year of reference end date, the it will be estimated by the first day of the month

If after imputation, the estimated end date is before the start date of the adverse event, it will be replaced by the start date of the adverse event.

6.4.5. Missing start/end dates of concomitant medications

Same rules as for adverse events.

7. STUDY SUBJECTS

7.1. Disposition of subjects

Screened subjects (signed informed consent) and included subjects will be summarised using frequencies and percentages as well as reasons of non-selection/non-inclusion, if applicable. The number and percentage of subjects who withdrew prematurely after inclusion, are lost to follow-up as well as the number of completers will be described.

All withdrawn subjects after their inclusion will be described regarding their main reason for withdrawal.

7.2. Protocol deviations

Protocol deviations will be discussed during the data review meeting and the status (minor or major) of these deviations will be validated in order to identify the subjects to be excluded from the PP set.

Major deviations are identified by:

- Non-compliance with the inclusion and exclusion criteria;
- Non-compliance with treatment;
- No collection of middle meatus swab sample at any visit;
- Intake of forbidden medication, i.e. nasal irrigation.

All other deviations will a priori be considered as minor.

All major and minor deviations related to study inclusion or exclusion criteria, conduct of the trial, subject management or subject assessment will be listed by subjects.

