8.3.1 Eligibility criteria

8.3.1.1 *Inclusion criteria*

In order to be eligible to participate in this study, an individual must meet all of the following criteria:

1. Male or female, aged $\geq 18 - \leq 70$ years
2. Provision of signed and dated informed consent form
3. Stated willingness to comply with all study procedures and availability for the duration of the study
4. Diagnosed with CRS based on the diagnostic criteria of the EPOS guideline
5. Registered with a social security scheme or covered by such a regime

8.3.1.2 *Non-inclusion Criteria*

An individual who meets any of the following criteria will be excluded from participation in this study:

1. Antibiotics or oral corticosteroids intake in the month prior to the study
2. Endoscopic sinus surgery in the 6 past months
3. Cystic fibrosis
4. Wegener's granulomatosis
5. Immunodeficiency
6. Defective access to the middle meatus
7. Lidocaine allergy
8. Known hypersensitivity/allergy to any component of the test device
9. Pregnant/Lactating female or absence of efficient contraception
10. Under tutorship or guardianship

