8.4.2 Permitted and forbidden concomitant medications

All concomitant medications are authorized during the investigation, except nasal irrigation, systemic corticosteroids, topical (nasal mucosa) and systemic antibiotics.

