11.7 Procedure for data retention

Once the Clinical Investigation Report is signed and validated, the data are archived on a dedicated hard disk file with limited access rights. This specific file is mounted on AXIODIS's OVH server with a

back-up every two months as well as copied to an external disk that will be stored under seal within the premises of AXIODIS. The data are conserved for at least 10 years.

12. Amendments to the CIP

Neither the investigator nor the sponsor may alter the protocol without the authorisation of the other party.

All changes to the protocol are subject to an amendment which must be dated and signed by both parties and must appear as an amendment to the protocol.

Substantial amendments are submitted to the EC and ANSM for approval.

13. Deviation from clinical investigation plan

All protocol deviations will be managed as per the Standard Operating Procedures of the CRO in charge of the study coordination.

A deviation log shall be maintained by the study site. All deviations will be included, as required in the final study report.

Any major deviation from the protocol that has not been previously approved by the sponsor must be reported to the sponsor within 2 working days of the deviation occurrence. Any deviations from the clinical investigation plan that are identified during routine monitoring visits will be reported to the sponsor within 24 hours of being identified.

Corrective and preventive actions and principal investigator disqualification criteria will be described in the monitoring plan.

Major protocol deviations are defined as deviations liable to prevent or change the interpretation of the results of the study. The following deviations are considered major:

- Non-compliance with the inclusion or exclusion criteria
- Non-compliance with treatment
- No collection of middle meatus swab sample at any visit
- Intake of forbidden medication

All other cases will, a priori, be considered as minor deviations.

14. Device accountability

Not applicable for this post market interventional study.

15. Ethical consideration

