4. SAMPLE SIZE

An arbitrary sample of 20 subjects completing the investigation without major protocol deviation has been chosen.

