5. DEFINITION OF THE ANALYSIS SETS

Screened subjects: all subjects who signed an informed consent

Included subjects: all screened subjects who will have been expected to participate in the study.

Safety Set: all subjects who will have used the investigational medical device at least once.

Full Analysis Set (FAS): all subjects from the Safety Set who will have at least one post baseline Sino Nasal Outcome Test-22 (SNOT-22) evaluation.

Per Protocol Set (PP): all subjects from the FAS without any major protocol deviation.

The status of protocol deviations (minor or major) will be validated during the data review meeting.

Any subject not satisfying major entry criteria or for whom post inclusion data are not available will be identified by the Validation Committee during the data review, and could be excluded from the FAS Set in agreement with circumstances exposed in the ICH-E9 §5.2.1.

Safety analysis will be performed on the Safety Set.

Efficacy analysis (except primary efficacy criterion) will be performed on the FAS.

Note: primary efficacy criterion (16S rRNA gene high throughput sequencing) will be analysed separately by a dedicated team specialized in microbiome analysis.

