12. CHANGES IN THE CONDUCT OF THE STUDY OR PLANNED ANALYSIS

After data review, considering no serious adverse event related to the nasal swab occurred, display of AE is split between 2 categories “incident related to the study device” and “AE not related to the study device” instead of the former 3 categories (incident, AE related to nasal swab procedure and AE related to chronic rhinosinusitis).

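### SAP 7.2 narrows the forbidden-medication major deviation to nasal irrigation, so on-study antibiotic or systemic corticosteroid use is minor by default and no supplied analysis tests its influence

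*SAP*

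**What the plan says.** Protocol section 8.4.2 allows all concomitant medication "except nasal irrigation, systemic corticosteroids, topical (nasal mucosa) and systemic antibiotics"; the synopsis names the same classes. Protocol section 13 lists "Intake of forbidden medication" among the major deviations without limiting it to one class, and gives the principle behind the list: "Major protocol deviations are defined as deviations liable to prevent or change the interpretation of the results of the study".

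SAP section 7.2 carries over the same four-item list but words the last item as "Intake of forbidden medication, i.e. nasal irrigation". Everything else is minor a priori, with final status validated at the data review meeting. SAP section 12, where changes are declared, has one entry, on adverse event tables ("display of AE is split between 2 categories"); it does not mention medication.

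SAP section 5 defines the per-protocol (PP) set as FAS subjects with no major deviation, but assigns it no analysis: "Efficacy analysis (except primary efficacy criterion) will be performed on the FAS". Section 10.1 sends the primary 16S analysis to a separate document and says its population will depend on how the sequencing turns out.

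**The concern.** The two documents classify the same event differently. Under the protocol, a patient given an antibiotic or a systemic corticosteroid between V1 and V2 is a major deviator. Under the literal SAP wording, that patient is a minor one.

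The SAP rule is also uneven. Intake in the month before entry breaches an eligibility criterion ("Antibiotics or oral corticosteroids intake in the month prior to the study") and so is major. The same intake between the two swabs, where it bears directly on the before/after difference, is minor by default.

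The study has one arm, no control group, and a primary endpoint of bacterial load and community profile. A change produced by an antibiotic during treatment cannot be separated from a device effect. With about 20 pairs, a few such patients can move the described average change, and nothing in the supplied text removes them or shows the result without them.

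**Working it through.** **Step 1: the texts side by side.**

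| Medication taken on study | Forbidden (protocol 8.4.2) | Major under protocol 13 | Major under SAP 7.2 as written |
|---|---|---|---|
| Other nasal irrigation | yes | yes | yes |
| Systemic corticosteroid | yes | yes | no, minor a priori |
| Nasal antibiotic | yes | yes | no, minor a priori |
| Systemic antibiotic | yes | yes | no, minor a priori |

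No other SAP bullet reliably catches the last three rows. The eligibility item covers only the month before the study. Protocol section 8.3.2 lets the investigator withdraw a participant who newly meets an exclusion criterion, but that is not a deviation class.

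**Step 2: what follows from the default.** Unless reclassified, these patients stay in the PP set, are absent from Listing 14.1.1.2 (major deviators), and count towards the target in SAP section 4: "An arbitrary sample of 20 subjects completing the investigation without major protocol deviation has been chosen". If k of 20 otherwise deviation-free patients are exposed, the PP set has 20 − k under the protocol and 20 under the SAP: 19 against 20 for k = 1, 18 for k = 2, 16 for k = 4. Tables 14.2.1 to 14.2.4 are all on the FAS, so no efficacy table changes either way.

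**Step 3: how likely is any exposure?** The plan has no figure to reproduce: N = 20 is called arbitrary, and no rate of use is given. For an assumed rate p, P(at least one of 20) = 1 − (1 − p)^20.

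| p | 2% | 5% | 10% | 15% | 20% |
|---|---|---|---|---|---|
| P(at least 1) | 0.33 | 0.64 | 0.88 | 0.96 | 0.99 |
| P(at least 2) | 0.06 | 0.26 | 0.61 | 0.82 | 0.93 |
| Expected number | 0.4 | 1 | 2 | 3 | 4 |

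**Step 4: size of the bias.** Assume no device effect and a drug-induced shift of 2 to 3 SD of the within-patient change, in the same direction for every exposed patient. Spurious mean change = (k/20) × shift.

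- k = 1: 0.05 × 2 to 3 = 0.10 to 0.15 SD
- k = 2: 0.10 × 2 to 3 = 0.20 to 0.30 SD
- k = 4: 0.20 × 2 to 3 = 0.40 to 0.60 SD

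The standard error of the mean change is 1/√20 = 0.224 SD, so k = 2 gives 0.20/0.224 = 0.9 to 0.30/0.224 = 1.3 standard errors. In simulation the median moved less: 0.13 to 0.14 SD for k = 2 and about 0.3 SD for k = 4.

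**Step 5: p-values.** Simulation of 20 bivariate normal pairs, 20,000 replicates per setting, two-sided 5% level, same shifts. Entries are rejection rates.

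| Test | Within-patient correlation | k = 0 | k = 2 | k = 3 | k = 4 |
|---|---|---|---|---|---|
| Rank-sum (protocol section 9) | 0 | 5% | 6–7% | 10% | 14–15% |
| Rank-sum | 0.3 | 2% | 4% | 6–7% | 10–12% |
| Rank-sum | 0.5 | under 1% | 2% | 3–4% | 6–8% |
| Signed-rank (paired) | any | at most 5% | 7–8% | 11–13% | 17–21% |

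At correlation 0.7 the rank-sum rate stays below 5% (about 0.5% for k = 2, 2–4% for k = 4). For k = 1 neither test moves from its no-exposure rate.

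**The case against.** The case against is about consequence, not wording.

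- **Minor is only a default.** The data review meeting validates every status, protocol section 11.6 requires evaluability decisions to be documented before lock, and the Latin abbreviation may be a slip for one meaning for example. This stands in part: the meeting can repair the classification. But the SAP gives it a default opposite to the protocol's, in an open-label study. Section 12 already records a change made after data review and says nothing about medication.
- **The PP set feeds no efficacy table.** This stands. Correcting the bullet alone changes a count, the deviation tables and a listing.
- **The count towards 20 has little operational force.** This stands. Subjects are not replaced, the number is arbitrary, and no recruitment rule depends on it.
- **The patients are not hidden.** True: Listing 16.2.2 shows all deviations and Table 14.3.1.3 tabulates concomitant treatments. For SNOT-22 a reader could trace individuals through Listing 16.2.6. That does not extend to the 16S data, and a listing is not a sensitivity analysis.
- **The microbiome document may deal with this.** It may, and it was not supplied. The point is therefore limited to the supplied text, where section 10.1 states no criterion; its wording may mean only technical quality control.
- **The magnitudes rest on assumptions.** They do, and they model one continuous outcome rather than PERMANOVA or LEfSe. SAP section 6.3.1 makes p-values informational, so the rejection rates carry little weight.

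**Conclusion.** The concern holds. The contradiction between SAP section 7.2 and protocol sections 8.4.2 and 13 is literal and undeclared. It puts on-study antibiotic and systemic corticosteroid use in the minor class by default, against the protocol's own definition of a major deviation. The accompanying gap matters more for the results: no supplied analysis excludes these patients or shows their influence on the before/after comparison.

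The size is conditional. With two exposed patients and the assumed shifts, the described mean change is off by roughly one standard error; with four, by about two to three (0.40/0.224 = 1.8 to 0.60/0.224 = 2.7). With none exposed there is no effect. The conclusion on the text needs no assumption; the figures rest on assumed exposure counts and a common 2 to 3 SD shift. The sponsor should correct this, but it does not invalidate an exploratory, descriptive study.

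**What to change.** 1. **SAP section 7.2.** Reconcile it with protocol sections 8.4.2 and 13 so that the major-deviation item covers every class the protocol forbids, or declare and justify the narrower rule in SAP section 12. If the review meeting has already reclassified any patient, record it there.
2. **SAP section 10.1 or the separate microbiome plan.** Fix the primary population before sequencing results are seen: subjects whose V1 and V2 swabs both pass a pre-stated sequencing quality criterion, such as a fixed minimum read count, applied without knowledge of visit. This does not itself address medication, but it gives the sensitivity analysis a defined starting set.
3. **SAP sections 5 and 10.** Add a sensitivity analysis that repeats the primary analysis (restricted to subjects of that population who are also in the corrected PP set) and the SNOT-22 analysis on the corrected PP set. Report how many subjects were removed and why. The main analyses stay as planned.

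The cost is one bullet, one population sentence and one repeat analysis. Concomitant medication is already collected at V1, TC1 and V2. The sensitivity set may lose a few pairs: going from 20 to 18 raises the standard error of the mean change by 5% (√(20/18) = 1.054), and to 16 by 12% (√(20/16) = 1.118).

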7.3. Data Sets Analysed

The number and percentage of subjects in each analysis data set, as described in §5, will be provided.

8. DEMOGRAPHIC AND OTHER BASELINE CHARACTERISTICS

Baseline safety characteristics will be described on the Safety Set.

All demographic and baseline characteristics (including safety characteristics) will be described on the FAS.

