8.5. Baseline safety variables

Adverse events since enrolment will be described at baseline.

Serious adverse events potentially related to the sino-nasal swab procedure will be described at baseline.

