13.2. List of statistical tables, figures and listings

Type	Number	Title
STUDY SUBJECTS		
Table	14.1.1.1	Subjects disposition [Screened subjects]
Figure	14.1.1.1	Subjects disposition [Screened subjects]
Listing	14.1.1.1	Not included / excluded subjects – Reasons [Screened subjects]
Table	14.1.1.2	Summary of protocol deviations [Included subjects]
Listing	14.1.1.2	Subjects with at least one major protocol deviation [Included subjects]
Table	14.1.1.3	Premature withdrawal – Reason of withdrawal [Included subjects]
Listing	14.1.1.3	Subjects prematurely withdrawn [Included subjects]
DEMOGRAPHIC AND OTHER BASELINE CHARACTERISTICS		
Table	14.1.2.1	Baseline – Demographic Characteristics [FAS]
Table	14.1.2.2	Baseline – Medical and surgical past history [FAS]
Listing	14.1.2.2	Baseline – Subjects with a medical or surgical history [FAS]
Table	14.1.2.3	Baseline – Number (%) of subjects with at least one previous or concomitant medication, by WHO-Drug ATC class and substance name [FAS]
Table	14.1.2.4	Baseline - SNOT-22 Symptoms of chronic rhinosinusitis scores [FAS]
Table	14.1.2.5.1	Baseline – Baseline safety variables – Adverse events since enrolment [FAS]
Table	14.1.2.5.2	Baseline – Baseline safety variables – Serious Adverse events potentially related to the sino-nasal swab procedure [FAS]
Table	14.1.2.6	Baseline – Other baseline variables [FAS]
EFFICACY		
Table	14.2.1	Secondary efficacy criteria – SNOT-22 score [FAS]
Table	14.2.2	Secondary efficacy criteria – Subject satisfaction [FAS]
Table	14.2.3	Secondary efficacy criteria – Symptoms of chronic rhino sinusitis [FAS]
Table	14.2.4	Secondary efficacy criteria – Weight of device [FAS]
SAFETY		
Table	14.3.1.1	Safety – Study duration by subject [Safety Set]
Table	14.3.1.2	Safety – Summary of compliance [Safety Set]
Table	14.3.1.3	Safety – Concomitant treatments [Safety Set]
SAFETY – Adverse events		

Type	Number	Title
Table	14.3.2.1	Safety – Brief summary of incidents related to the use of the medical device [Safety Set]
Table	14.3.2.2	Safety – Brief summary of adverse events not related to the use of the medical device [Safety Set]
Table	14.3.2.3	Safety – TEAE (incidents) related to the use of the medical device by System Organ Class and preferred term [Safety Set]
Table	14.3.2.4	Safety – TEAE not related to the use of the medical device by System Organ Class and preferred term [Safety Set]

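### The two baseline safety tables, including the one for swab-related serious events, are planned only on the FAS, so the Safety Set display promised in SAP Section 8 has no table.

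*SAP*

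**What the plan says.** SAP Section 8 gives two instructions in succession. The first is "Baseline safety characteristics will be described on the Safety Set". The second is "All demographic and baseline characteristics (including safety characteristics) will be described on the FAS".

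SAP Section 8.5 names the variables concerned: "Adverse events since enrolment will be described at baseline" and "Serious adverse events potentially related to the sino-nasal swab procedure will be described at baseline".

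The table list in SAP Section 13.2 has one table for each, 14.1.2.5.1 and 14.1.2.5.2. The second is titled "Baseline – Baseline safety variables – Serious Adverse events potentially related to the sino-nasal swab procedure [FAS", the bracket giving the population. The mock tables in Section 13.3 carry the same label.

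SAP Section 5 defines the Safety Set as "all subjects who will have used the investigational medical device at least once". It defines the FAS as the members of that set with at least one SNOT-22 after baseline. The same section assigns safety analysis in general to the Safety Set.

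**The concern.** The middle meatus swab is the study's additional invasive procedure and has its own reporting route for serious events (Protocol 16.3.2 and 16.4.2). A table of harm around that procedure should count everyone who underwent it, or at least everyone in the Safety Set. The planned tables instead depend on a quality-of-life form completed later. Stopping early because of an event is one way to miss that form, so the tables may omit subjects whose events they are meant to show. The first row of mock Table 14.1.2.5.1 counts incidents and the next counts incidents leading to definitive device discontinuation. For that second row, a population that requires a post-baseline SNOT-22 fits poorly.

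**Working it through.** The plan states no figure on this point, so the check compares the passages and adds one illustration.

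**Step 1: count the displays.** Baseline safety tables in SAP 13.2: 2. On the FAS: 2. On the Safety Set: 0. The mocks in 13.3 agree. The second sentence of Section 8 is therefore carried out and the first is not.

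**Step 2: who can be in the Safety Set but not the FAS.** SNOT-22 is scheduled only at V1 and V2 (Protocol 8.1.5.2 and the flow chart), so there is one scheduled post-baseline assessment. Protocol 8.3.2.1 plans a premature end-of-study visit for withdrawn subjects, but the documents do not say whether SNOT-22 is done there.

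**Step 3: who can be swabbed but outside both sets.** In the V1 sequence of Protocol 8.4.1 the swab comes before the device is handed over, and use is at home. A subject swabbed at V1 who never sprays fails the Safety Set definition and so the FAS definition.

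| Subject, all swabbed at V1 | Tables 14.1.2.5.1 and 14.1.2.5.2 (FAS) | Section 11 outputs (Safety Set) |
|---|---|---|
| Treated, second SNOT-22 obtained | counted | counted |
| Treated, leaves, no second SNOT-22 | missing | counted |
| Never uses the device | missing | missing |

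**Step 4: where else swab events would be visible.** SAP 11.2 still mentions a table of treatment-emergent events related to the swab. Section 12 then replaces the former three categories by two, device-related and not device-related, and Section 13.2 lists no swab-related treatment-emergent table. Table 14.1.2.5.2 is thus the only listed table dedicated to swab events. Tables 14.3.2.1 to 14.3.2.6 cover events on the Safety Set, split only by relation to the device. The reference start date is the inclusion visit (SAP 6.4.1), so a new event starting at V1 meets the treatment-emergent definition in 11.2 and would appear there, without a swab label.

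**Step 5: illustration.** Assume 20 treated subjects and one event, in a subject who leaves without a second SNOT-22. The figure 20 is borrowed from SAP Section 4, where it is the number completing without major deviation, so the treated number may differ. The limits are exact (Clopper-Pearson) 95% limits, which the SAP does not plan; for zero events the upper limit is 1 − 0.025^(1/n).

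- Safety Set: 1/20 = 5.0% (0.1% to 24.9%).
- FAS with 1 leaver: 0/19 = 0%, upper limit 1 − 0.025^(1/19) = 17.6%.
- FAS with 2 leavers: 0/18, upper limit 18.5%.
- FAS with 4 leavers: 0/16, upper limit 20.6%.

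**Step 6: apply Section 12.** Section 12 states that no serious event related to the swab occurred. On that statement the numerator of Table 14.1.2.5.2 is zero on any set. Only the denominator moves: with 20 subjects the upper limit is 1 − 0.025^(1/20) = 16.8%, against 17.6% with 19. Table 14.1.2.5.1 covers non-serious events too, so its numerator can still differ between sets.

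**The case against.** The strongest reply is that the FAS tables do what the SAP asks, because the second sentence of Section 8 names the FAS for safety characteristics expressly. This stands, and it means the FAS tables are not themselves an error. It does not supply the Safety Set display. Either both displays are intended and one has no table, or the two sentences conflict.

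A reader might infer that the FAS table hides a serious swab-related event. The documents do not support that, since Section 12 says none occurred.

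A reader might also infer that anyone harmed by the swab who stops is certain to be outside the FAS. That does not follow. If SNOT-22 is completed at the premature end-of-study visit, the subject stays in. Nor do the documents give any figure showing that those who leave early are the likeliest to have been harmed; Protocol 6.3 expects no risk from the procedure.

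Finally, treated subjects' events are not lost to the report. They reach the Section 11 Safety Set tables, and Section 11.2 also promises listings of serious events and of events leading to discontinuation. Related serious events follow their own reporting route whatever the analysis set. All of this stands and limits the point, but those tables do not identify an event as swab-related, and Section 11 is confined to the Safety Set, so it does not cover a subject who was swabbed and never treated.

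**Conclusion.** The point holds as a gap between the SAP text and its table list. Section 8 promises baseline safety on the Safety Set, and neither of the two tables provides it. The practical effect is small. For swab-related serious events it is confined to the denominator, on the strength of the statement in Section 12. For adverse events since enrolment, events in treated subjects with no second SNOT-22 can drop out of the baseline table, though not out of the Section 11 tables. How many subjects this concerns is unknown: it depends on early departures, on whether SNOT-22 is obtained at the premature visit, and on whether anyone was swabbed and never treated. The comparison of 5.0% with 0% shows how one subject matters at this sample size; it is not an estimate of what happened.

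**What to change.** In SAP 13.2 and 13.3, produce Tables 14.1.2.5.1 and 14.1.2.5.2 on the Safety Set. Adding them beside the FAS versions satisfies both sentences of Section 8. Replacing the FAS versions also requires amending the second sentence. In either case reword Section 8 so that the set for baseline safety is unambiguous.

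For Table 14.1.2.5.2, preferably use all included subjects who had the V1 swab. SAP Section 5 has no such set, so define it there. A zero for the invasive procedure is then stated over everyone exposed to it.

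Because the SAP already refers to the data review, record the change in Section 12. The cost is one or two extra table runs and one added definition. No endpoint, significance level or sample size is affected.
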